#### 6.1.5 Inclusion/exclusion criteria

Patients will be considered eligible provided they meet all Inclusion/Exclusion criteria (See Sections 5.2 and 5.3 on Pages 14 and 15). The CRF will be documented accordingly.

#### 6.1.6 Demography/immunisation status

Demographic data including details of residential status, smoking habits, alcohol consumption, household contacts, immunisation status (influenza and pneumococcus during the previous 3 years), and hospital admissions during the period  $1^{st}$  September –  $30^{th}$  April of the previous winter will be recorded in the CRF.

#### 6.1.7 Medical history/regular medications

Details of the patients' concurrent medical conditions and regular medications will be obtained from the patient, and/or the medical practitioner's referral letter, and/or the admission clerking, and/or hospital notes, and/or family member/or carer, and will be recorded in the CRF.

#### 6.1.8 Presenting symptoms and the interval between their onset and admission

Details of the patient's current symptoms and symptoms that appeared during the 168 hours (7 days) before consultation will be recorded in the patient's CRF together with the medical practitioner's referral diagnosis. The date and time of admission to the Medical Admissions Unit will be recorded in the CRF. NOTE: Patients should not have new symptoms of >168 hours duration.

#### 6.1.9 Clinical findings

The Study Nurse will record pertinent clinical findings including blood pressure, pulse, jugular venous pressure, oedema, respiratory rate, breath sounds, oxygen saturation, and temperature in the CRF, by reference to the examination findings documented in the medical case notes. Details of body weight and height will also be obtained if possible, either on admission, or subsequently.

#### 6.1.10 Quality of Life assessment

All patients will be assessed by the EuroQol (Appendix I) on admission, (by proxy if they are incapable of completing the self-administered questionnaire or providing a verbal response) and the findings entered into the CRF.

#### 6.1.11 Investigations ordered by the admitting medical team

The study nurse will record in the CRF the diagnostic studies (e.g., full blood count, routine biochemistry, blood sugar, cardiac enzymes, d-dimers, chest radiograph, ECG, oxygen saturation, blood gases, urinalysis, antibody studies, blood, sputum, and urine cultures, viral culture, antigen tests, etc) that were carried out by the on-call medical admissions team.

#### 6.1.12 Antimicrobial and antiviral treatments prescribed

The Study Nurse will record in the CRF the names, route of administration, dose, frequency, and time of first administration of any antimicrobial or antiviral treatment that is prescribed by the responsible medical team during the first 24 hours of admission. Since it is possible that the patient may be seen by the Study Nurse before medication has been prescribed, it is essential that the medication given to the patient is constantly reviewed by the Study Nurse (See Section 6.2.2).

#### 6.1.13 Randomisation and Trial Identification Numbers

Patients in each centre will be randomly allocated, using computer generated randomisation codes stratified by centre, to one of three diagnostic study groups:

Group 1: Rapid near patient diagnostic tests (influenza and pneumococcus),

Group 2: Rapid molecular tests (influenza & RSV), plus laboratory pneumococcal antigen testing, and Group 3: Traditional 'laboratory culture' (influenza, RSV, and *S. pneumoniae*)]

The randomisation code (i.e., whether in Group 1, 2, or 3) will be included in sequentially numbered study packs that will be stored at each hospital (Leicester Royal Infirmary, Glenfield Hospital, and Leicester General Hospital). The Packs will be labelled as follows:

1-0001, etc, (Leicester Royal Infirmary site One)

**2**-0001, etc, (Glenfield Hospital siteTwo)

**3**-0001, etc, (Leicester General Hospital site Three) which correspond to the Trial Identification Numbers allocated to participants at each study site.

The randomisation codes will be generated by the Department of Health Sciences, University of Leicester. The randomisation code will not be known by the Study Nurse until after the patient has signed the Patient Informed Consent Form. Only then will the study pack containing details of randomisation be opened.

#### 6.1.14 Specimen collection and handling, and completion of investigation request forms

The sequentially numbered study packs will contain details of the randomisation code (See 6.1.11). Identical samples will be taken from each person, but samples for Study Groups 1, 2, and 3 will be processed differently depending on the participant's diagnostic study group. The following samples will be collected, and the time when ALL specimens were collected will be recorded in the CRF:

#### 1. BLOOD

A 20 ml blood sample will be collected from all study participants for:

- (i) Blood cultures 10mls of blood will be drawn by peripheral venepuncture for blood cultures. Blood culture bottles are routinely available in the MAU and acute medical wards. The blood culture bottles and investigation request form will be labelled with the patient's details (i.e., name, hospital number, and date of birth) in the standard way, BUT in addition with the participant's unique trial code and Study Group. Inclusion of the participant's name on both the label and request form should eliminate any confusion that might arise from use of a trial code alone. This sample may be additional to any blood culture investigation done by the medical team caring for the patient, but will be processed in the same way. The Investigation Request Form will be labelled with 'HTA Respiratory Infection Study'. The blood culture bottles and request forms will transported to the Clinical Microbiology Department using the routine transport arrangements.
- (ii) Blood for antibody studies A 10-ml blood sample will be collected. The bottle will be labelled with the participant's unique trial code, date of collection, patient initials, and date of birth only, i.e., not with the participant's name. The Investigation Request Form will be labelled with 'HTA Respiratory Infection Study'. This sample will be additional to any acute serum sample that is collected by the medical team caring for the patient, and it will be processed differently. The blood sample will be transported to the Clinical Microbiology Department using the routine transport arrangements.

#### 2. NASOPHARYNGEAL SPECIMENS

One (1) nasal, and one (1) nose and throat swab sample will be collected from all study participants. (See Appendix VIII) The nasal swab can be found in the The Quidel QuickVue Influenza A+B test kit, which is included in the sequentially numbered study packs. Similarly, nose and throat swabs for collection of nasopharyngeal specimens will be found in the participant's study pack. They will be used as follows:

• **GROUP 1 ONLY**: The swab in the Quidel QuickVue Influenza A+B test kit will be used in *one nostril only*, specifically to collect a nasal sample – for rapid near patient testing, in the MAU/ward, of participants in Group 1.

Patients randomised to Group 1 will have near patient tests for influenza A and B antigen done by the study nurse in an area of the MAU/ward where clinical tests such as urinalysis are done routinely. The instructions for collecting the Quidel QuickVue nasal sample and doing all tests are provided in Appendix IX. On completion of the test the Study nurse will:

- (a) Record the test result in the CRF;
- (b) Inform the team (i.e., the responsible nurse and/or doctor) that is providing clinical care of the patient of the rapid near patient test result (i) verbally; and (ii) by insertion of an adhesive label in the notes. The clinical team should be told that a negative test does not exclude infection with influenza A or B.
- (c) Document in the CRF the time that the team was informed, and who was told.
- **GROUPS 1, 2, and 3**: The nose and throat swabs for the molecular tests and traditional tissue culture studies (for influenza and RSV) will be used to swab the throat and *the opposite nostril* (i.e., ONE nostril only) to that used previously and placed in virus transport medium. The instructions for collecting the nose and throat sample are provided in Appendix VIII. The nose and throat sample will be collected from ALL study participants, specifically for:
  - Prompt, conventional viral culture (Groups 1, 2, and 3);
  - Prompt, rapid molecular testing for influenza A and B and RSV A and B (Group 2);
  - Deferred, molecular testing for influenza A and B and RSV A and B (Groups 1 and 3);
  - Deferred Quidel QuickVue test for influenza A and B (Groups 1 and 2)
  - Possible future tests for other respiratory pathogens of stored specimens, if tests for influenza, RSV, and *S. pneumoniae* are negative.

All tests will be done on samples collected from the participant's nose and throat using the swabs provided in individual patient Study Packs. The throat swab will be collected by vigorously rubbing the tonsils, soft palate, and back wall of the lower pharynx with the dry swab provided. The second nasal swab specimen should be collected from the participant's other nostril, i.e., NOT the nostril swabbed previously for the Quidel QuickVue near patient influenza A and B test, using the procedure described in Appendix IX. The swab tips are agitated in screw-capped study vials containing Virus Transport Medium, and are then cut off, or broken off, into the medium. The vials containing the nasopharyngeal specimen will be labelled with the participant's unique trial code corresponding to the sequentially numbered study pack. The Investigation Request Form will be labelled with 'HTA Respiratory Infection Study'. The specimens will be collected from in patients if their initial swabs are positive on day 2 or 3.

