### ANALYSIS

The sample size is based on the admissions during 2002-03 and 2003-04 (September 1 – April 30) for elderly ( $\geq$ 65 years old) patients with acute cardio-pulmonary conditions, excluding angina and myocardial infarction. There were 2762 acute cardio-pulmonary admissions during September 1 – April 30 2002-03, and 2852 during 2003-04, i.e., an average of 11.57 admissions ( $\geq$ 65 years) per day.

The study will run for at 666 days (242 during each of Years 1 and 2, and 183 during Year 3), i.e., the number of eligible patients is estimated at 666x11.57=7705.6. We plan to recruit 5 days per week, which reduces the eligible number of patients to  $(5\div7)x7705.6=5504$ . We understand that two-thirds are admitted during the period 09:00-21:00h, which reduces the evaluable pool to 3669. We estimate that three-quarters of eligible subjects will participate, i.e., we expect to recruit 2752 elderly ( $\geq 65$  years old) patients with acute cardio-pulmonary conditions. Of these, 664 are expected to have ICD codes for pneumonia; 556 are expected to have exacerbations of chronic obstructive pulmonary disease; and 735 are expected to be admitted with heart failure.

We estimated the number of admissions in 'high-risk' 18-64 year-olds by extrapolation using (i) national cardio-pulmonary hospital admission data for patients aged 15-59 years, 60-74 years, and 75 years and older and (ii) the number of cardio-pulmonary admissions aged  $\geq$ 65 years in Leicester.

	We assumed that half of the patients admitted with pneumonia, unspecified lower respiratory tract infections, and exacerbations of COPD have underlying high-risk conditions. We expect to recruit 83 18-64-year old patients with pneumonia, 93 with unspecified lower respiratory tract infections, and 181 with COPD. These have not been included in the following estimates: On the basis of historical data we expect that one-third of elderly patients with pneumonia have pneumococcal disease (i.e., 221) but expect the
	number identified by the pneumococcal antigen test to be higher. Of the 221, ~73 should be randomly allocated to the rapid near patient test (Binax NOW) (Group 1); the remainder will be randomised to the group tested by traditional methods (Groups 2 & 3). However, as identical sample sets will be taken from each individual, diagnostic accuracy will be assessed in a minimum of 221 subjects.

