#### 4 STUDY DESIGN

#### 4.1 Overall design

The study is a prospective, randomised controlled trial to evaluate the impact of rapid diagnostic testing for influenza, respiratory syncytial virus and *Streptococcus pneumoniae*, on the management and outcome of acute cardio-pulmonary admissions in the elderly (age  $\geq 65$  years), and 'high-risk' individuals (have underlying chronic heart or lung disease, including asthma) who are 18-64-years of age. Or Pneumonia / influenza type symptoms.

Patients who present to Medical Admissions' Units in Leicestershire with an acute exacerbation of chronic cardio-pulmonary illness of  $\leq$ 168 hours (7 days) duration, OR an acute cardio-pulmonary illness of  $\leq$ 7 days duration (including: pneumonia; 'influenza'/influenza-like illness; 'exacerbations of chronic obstructive pulmonary disease' (COPD); bronchitis; asthma; congestive heart failure; or cardiac arrhythmia), who satisfy the study inclusion and exclusion criteria (See Sections 5.2 and 5.3), and can be recruited to the study within a 16-hour period of initial assessment by a doctor on the Medical Admissions Unit or another ward accepting acute medical admissions, will be randomised to one of three groups:

Group 1: Rapid near patient diagnostic tests (influenza and pneumococcus), Group 2: Rapid molecular tests (influenza & RSV), plus laboratory pneumococcal antigen testing, and Group 3: Traditional 'laboratory culture' (influenza, RSV, and *S. pneumoniae*)]

All tests will eventually be done on all patients who enter the study, but patients in Groups 1 and 2 will only be provided with rapid test results relating to their randomisation group.

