- Based on the above, we expect to recruit 747 participants with pneumonia, of whom at least one third (n=249) should have *S. pneumoniae* infection. Of these, ~83 should be randomly allocated to the rapid near patient test (Binax NOW); the remainder will be randomised to the group tested by traditional methods. Thus the speed of diagnosis, impact of early diagnosis on prescribing, clinical outcomes, and costs will be assessed in groups having an estimated 83 and 166 subjects. However, as identical sample sets will be taken from each participant, the diagnostic accuracy of the tests will be assessed in all 249 subjects. The number of cases of *S. pneumonaie* infection that are likely to be identified among the anticipated 649 (556 +93) participants with unspecified acute lower respiratory tract infections is unknown, but their occurrence will add to the pool of cases for studies of diagnostic accuracy.
- On the basis of the Rochester study, we expect that 10% of the 2752 elderly (≥65 years) participants will have influenza A or B. Of the 275, one third (~92) will be allocated to the QuickView near patient influenza immunoassay; one third will be allocated to the rapid molecular group; the remainder will be allocated to the group tested by traditional methods. Identical sample sets will be taken from each individual, so the diagnostic accuracy of the tests will be assessed in all 275 subjects.
- Similarly, we expect that 5% of the 2752 elderly (≥65 years) participants will have RSV A or B. Of the 138, one third (~46) will be allocated to the rapid molecular group; the remainder (~92) will be allocated to the group tested by traditional methods. We expect that very few of these will be found

positive by the routine tests employed. Identical sample sets will be taken from each individual, so the diagnostic accuracy of the tests will be assessed in all 138 subjects.

While the numbers of patients with influenza and RSV who are allocated to the 'rapid' near patient or molecular tests are comparatively small (~92 + ~46 per elderly group, plus cases occurring in the 18-64-year-olds), the impact of a 'viral' infection (RSV or influenza) infection on patient isolation, antimicrobial prescribing, and clinical outcomes may be compared using a larger combined group – i.e.,

Elderly

Rapid influenza & RSV (i.e., Quickview + molecular tests) n=(92+92+46)=230Traditional influenza & RSV n=(92+46+46)=184

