#### Year 2: I June 2006 - 31 May 2007

- June August 2006: Carry out PCR, serology, & analysis of stored urine specimens; Audit and analysis of Year 1 data: purchase diagnostic kits and other consumables for second year. Prepare Year 1 analytical report.
- 2. **1 September 14 December 2006:** Collate and analyse all diagnostic data from Year 1, including serological data; Prepare Year 1 analytical report by 14 December 2006.
- 3. **1 September 2006 30 June 2007:** Year 2 clinical trial; continue with ongoing audit of patient recruitment, data entry into CRFs.
- 4. February 31 May 2007 Carry out 'Ease of test' study during February-May.
- 5. Nov 2006, Jan 2007, Mar 2007, May 2007: Review by Trial steering Committee of progress of Year 1 and 2 data.

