# SAMPLE TRANSPORT AND STORAGE

Samples should be tested as soon as possible after collection. Do not use any kind of transport media to store or transport samples. Samples may be stored refrigerated (2–8°C), or at room temperature (15–30°C), in a clean, dry, closed container for up to eight hours prior to testing.

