#### URINE (for diagnosis of pneumonia)

Collect urine specimens in standard containers. Store at room temperature (59-86°F, 15-30°C) if assayed within 24 hours of collection. Alternatively, store urine at 2-8°C or frozen for up to 14 days before testing. Boric acid may be used as a preservative.

When necessary, ship urine specimens in leakproof containers at 2-8°C or frozen.

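### The 275 and 221 accuracy denominators do not hold for QuickVue or for either form of Binax NOW, because deferred testing misses groups and departs from the appended kit instructions

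*Protocol*

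**What the plan says.** **The promise.** Protocol section 4.1 states: "All tests will eventually be done on all patients who enter the study". Section 7.1 says of influenza that identical samples are taken, "so the diagnostic accuracy of the tests will be assessed in all 275 subjects". The synopsis (sample size) says of pneumococcal disease that "diagnostic accuracy will be assessed in a minimum of 221 subjects".

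**QuickVue.** In section 6.1.14 Group 1 has the ward test on the nasal swab from the kit. For all groups, further swabs are taken from the throat and the opposite nostril "to that used previously and placed in virus transport medium". One of the tests listed for that sample is "Deferred Quidel QuickVue test for influenza A and B (Groups 1 and 2". Appendix IX asks for the kit's own swab, says "Do not use any kind of transport media to store or transport samples", and allows at most eight hours in a dry, closed container.

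**Binax NOW.** Section 6.1.14 gives Group 1 the ward test, with no mention of concentration. Group 2 has prompt laboratory testing of fresh concentrated urine, and Group 3 has deferred testing of stored concentrated urine. Appendix X lets urine be kept at 2–8°C "or frozen for up to 14 days before testing".

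**Timing.** Section 9, for June to August 2006, reads: "Carry out PCR, serology, & analysis of stored urine specimens". Under Year 3 the same work is set for May to August 2007 and again for January to March 2008. Section 9 gives no date for the deferred QuickVue.

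**The concern.** Diagnostic accuracy is objective 1 in section 2.1, and the protocol rests its precision on the argument that identical sampling lets every test be assessed in every case. That argument fails if a test is not scheduled in a group, or is run on a specimen that its own instructions exclude.

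Two things are at stake. First, the usable number of cases for the near-patient tests is smaller than stated, so their sensitivity will be known less precisely. Second, if ward results are pooled with results from transport-medium swabs or long-stored urine, the pooled figure describes no defined test. Sections 6.1.14 and 9 fix the specimen, the groups and the timing, so this is not a detail left for a later analysis plan.

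**Working it through.** **1. The protocol's counts.** From the synopsis: 666 days × 11.57 admissions × 5/7 × 2/3 × 3/4 = 2752. Influenza at 10%: 2752 × 0.10 = 275.2. Pneumococcal disease in one third of 664 elderly pneumonia cases: 664/3 = 221.3. Both stated figures reproduce.

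**2. The protocol's precision.** The formula is 2 × √(p(1−p)/n), with n = cases × 0.8 for 20% dropout.

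- 10% prevalence: n = 2752 × 0.8 × 0.10 = 220.2; 2 × √(0.16/220.2) = 5.4 points.
- 5% prevalence: n = 110.1; 2 × √(0.16/110.1) = 7.6 points.

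Section 7.4 prints 7.6% for 10% prevalence and 5.4% for 5%, so its prevalence labels appear to be swapped. That is a separate error. The comparators below are recomputed values, not printed ones.

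**3. Cases per test as scheduled.** Equal thirds per group, as the protocol assumes.

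| Test and specimen | Groups | Cases | After dropout | 2SE, 80% | 2SE, 90% |
|---|---|---|---|---|---|
| Influenza, full count | 1, 2, 3 | 275 | 220.2 | 5.4 | 4.0 |
| QuickVue as listed | 1, 2 | 183 | 146.8 | 6.6 | 5.0 |
| QuickVue, specimen the kit allows | 1 | 92 | 73.4 | 9.3 | 7.0 |
| Pneumococcus, full count | 1, 2, 3 | 221 | 176.8 | 6.0 | 4.5 |
| Binax, concentrated urine | 2, 3 | 147 | 117.9 | 7.4 | 5.5 |
| Binax, ward test | 1 | 74 | 58.9 | 10.4 | 7.8 |

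For example, 2 × √(0.16/73.4) = 9.3 points and 2 × √(0.16/58.9) = 10.4 points. Of the 147 concentrated-urine cases, about 74 (Group 2) are on fresh urine and about 74 (Group 3) on stored urine.

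If the QuickVue list is read as Groups 2 and 3, the count returns to 275. About 183 of those would still be transport-medium samples.

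**4. Age of stored urine.** Year 1 recruitment runs from 1 September 2005 to 30 June 2006 (303 days), and testing starts on 1 June 2006 at the earliest. A sample from 1 September 2005 is then 273 days old. Any sample taken before 18 May 2006 is past 14 days, which is 259/303 = 85% of the Year 1 calendar. For Year 2, with testing from 1 May 2007 at the earliest, the share is 228/303 = 75%. These are minimum shares, because they take the first day of each window.

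**5. Adding the 18–64-year-olds.** Section 7.1 gives 83 pneumococcal cases in Group 1 over all ages: n = 83 × 0.8 = 66.4, so ±9.8 points. With about 38 more influenza cases, Group 1 has (275.2 + 38)/3 = 104.4; n = 83.5, so ±8.8 points. The conclusion does not change.

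**The case against.** Much of the case on the other side narrows the point, and several parts of it stand.

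- **The group list is probably a slip.** Group 1 already has the ward test, so Groups 2 and 3 were most likely meant. This cures the missing group only. The transport-medium, swab and eight-hour conflicts remain.
- **The totals are not lost for every test.** A reader might infer that accuracy in 275 and 221 cases cannot be delivered at all. The documents do not support that. PCR (prompt in Group 2, deferred in Groups 1 and 3) and viral culture are scheduled in all three groups, so 275 stands for PCR. Some form of Binax reaches all 221. What fails is QuickVue, and any single form of Binax. The protocol itself costs ward and concentrated-urine Binax as separate tests.
- **The deferred results are not shown to be invalid or biased downwards.** The kit texts set handling limits. Breaching them makes a result off-kit. A loss of sensitivity is plausible, but no passage shows its direction or size.
- **The storage breach is inferred.** It comes from the batch calendar and concerns Group 3 alone. No storage temperature or interval per sample is given.
- **The precision figures depend on the choice of case.** At 90% sensitivity they are milder. Specificity suffers less: Group 1 has 2752/3 × 0.8 × 0.9 = 660 non-influenza patients, or ±3.1 points at 80%.
- **The randomised comparisons over all patients** rest on results released by group, which deferred testing does not alter. The point should not be stretched to them.

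**Conclusion.** The concern holds for QuickVue and for each form of Binax NOW, and not for PCR or culture. The promise of all tests in all patients, and the denominators of 275 and 221, conflict with sections 6.1.14 and 9 and with the appended kit instructions.

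Kit-conformant QuickVue rests on about one third of the stated influenza cases and ward Binax on about one third of the stated pneumococcal cases. At 80% sensitivity, two standard errors rise by a factor of about 1.7 (√3) in each. The ±9.3 points for QuickVue is also worse than the 7.6% that the protocol prints for 10% prevalence. Concentrated-urine Binax keeps about two thirds of its cases, half of them on stored urine that is mostly past the limit.

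This rests on equal allocation, the protocol's own prevalences, 20% dropout, elderly patients only, and the batch calendar as the true testing date.

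**What to change.** 1. In section 7.1, section 7.4 and the synopsis, give the denominator and precision separately for each test and specimen type. Keep 275 for PCR.
2. Make Group 1 the main accuracy set for near-patient QuickVue and ward Binax.
3. Report QuickVue on transport-medium samples, and Binax on urine stored beyond 14 days, apart as off-kit results. Do not pool them with ward results.
4. Correct the group list for deferred QuickVue. Section 6.1.14 says that a nasal swab is taken from everyone and then restricts the kit swab to Group 1; reconcile the two.
5. For urine still to be collected, test Group 3 in batches within 14 days, with results withheld from the clinical team.

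**Cost.** Items 1 to 4 are wording and reporting and need no extra patients, but the stated precision becomes less favourable. Item 5 means more frequent batches. Version 6 is dated November 2007, after two of the three recruitment seasons, so Year 1 and Year 2 samples can only be reported separately. Running QuickVue within eight hours on dry kit swabs in Groups 2 and 3 would be a larger step: about 2752 × 2/3 = 1,835 extra tests over the whole elderly sample, with results that must be kept from the wards. It is not needed for this correction.
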